2.2. Safety Endpoint

The primary safety endpoint is evaluated by tabulations of adverse events.

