- Program safety. Recognition that certain programs are not appropriate for certain situations. E.g. Program 4 is a directional microphone program and thus is not appropriate for driving a car due to compromised awareness of sound behind you such as sirens.

Part Two: Clinical Testing Protocol: Laboratory Evaluation of Validity of MDHearing Self-Fitting Method

- Subjects:
 - 75 subjects with mild to moderate sensorineural hearing loss.
 - Subjects will not be allowed to participate if they have any signs of middle or outer ear infection or abnormality.
 - All subjects will undergo a hearing evaluation to ensure they do not have any of the following conditions:
 - Visible congenital or traumatic deformity of the ear.
 - History of active drainage from the ear in the previous 90 days.
 - History of sudden or rapidly progressive hearing loss within the previous 90 days.
 - Acute or chronic dizziness.
 - Unilateral hearing loss of sudden or recent onset within the previous 90 days.
 - Audiometric air-bone gap equal to or greater than 15 decibels at 500 Hz, 1,000 Hz, and 2,000 Hz.
 - Visible evidence of significant cerumen accumulation or a foreign body in the ear canal.
 - Pain or discomfort in the ear.
 - At least one air conduction threshold must be above 25dB. All air conduction thresholds must be below 60db.
 - Subjects will be at least 18 years old. There are no other limits on subject age.
- Protocol and ANSI specs
 - Subjects take the personalization profile on an iPad tablet.
 - Subjects then listen to the same recorded speech passage at their Most Comfortable Listening level 3 times and adjust the aids for comfort (volume, bass, treble, and mid) while the passage is playing. Subjects do not have to make changes if they are content with the sound quality.
 - After each passage, Real Ear measurements will be taken. Gain results at 500, 1000, 2000, and 4000Hz for a 60dB input will be recorded.

• The differences between gain for each frequency will be evaluated per subject. See table below for example:

Subject		500Hz	1000Hz	2000Hz	4000Hz	Total gain
1						deviation
	Passage 1	15dB	18dB	20dB	23dB	
	Passage 2	17dB	19dB	22dB	22dB	
	Passage 3	14dB	18dB	19dB	24dB	
	Average	2.5	1	2.5	1.5	1.9dB
	deviations					

Part Three: Comparative Clinical_Testing Protocol: Clinical Validation of MDHearing Self-Fitting Method

- Subjects
 - 75 subjects with mild to moderate sensorineual hearing loss.

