 - Subjects must have and be able to use a smartphone that is compatible with the MDHearing app.
 - Subjects will not be allowed to participate if they have any signs of middle or outer ear infection or abnormality.
 - All subjects will undergo a hearing evaluation to ensure they do not have any of the following conditions:
 - Visible congenital or traumatic deformity of the ear.
 - History of active drainage from the ear in the previous 90 days.
 - History of sudden or rapidly progressive hearing loss within the previous 90 days.
 - Acute or chronic dizziness.
 - Unilateral hearing loss of sudden or recent onset within the previous 90 days.
 - Audiometric air-bone gap equal to or greater than 15 decibels at 500 Hz, 1,000 Hz, and 2,000 Hz.
 - Visible evidence of significant cerumen accumulation or a foreign body in the ear canal.
 - Pain or discomfort in the ear.
 - At least one air conduction threshold must be greater than 25dB. All air conduction thresholds must be less than 60db.
 - Subjects will be at least 18 years old. There are no other limits on subject age.
- First visit
 - A hearing test is performed on all subjects.
 - Subjects complete the Abbreviated Profile of Hearing Aid Benefit (APHAB) and Speech, Spatial, and Qualities of Hearing Scale (SSQ-12).
 - Subjects complete the Quick SIN. (Speech in Noise test)

- All subjects use the MDHearing CORE with the tubing and ComfortTIP that is appropriate for their hearing loss. The tubing and ComfortTIP selection is audiologist fit to half the participants. The other half of the participants chose their own tubing and ComfortTIP. The tubing options are thin tubing with open ComfortTIP or thin tubing with closed ComfortTIP.
- The subjects are split into two groups.
 - The groups are controlled for demographic such as age, gender, length of hearing loss, previous hearing aid use, length of hearing aid use, comfort with technology and level of sensorineural hearing loss.
- Half of the subjects take the MDHearing personalization profile and are fit using NAL NL
 2 fitting software embedded in the MDHearing app. (Self-fit group)
- Half of the subjects are fit using hearing aid fitting software with the NAL NL 2 fitting method. (Audiologist fit group)
- The subjects that are self-fit have access to changing their volume control, programs, bass, treble, and mid pitched settings, noise reduction, and microphone direction using the MDHearing app.

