- The subjects that are audiologist fit have access to changing their volume control and programs on the CORE hearing aid. The audiologists have access to changing the bass, treble, and mid pitched settings, noise reduction, and microphone direction using the fitting software.
- Wearing period
 - Subjects wear the hearing aids for one month to acclimate. Minimum of 8 hours per day usage is required.
 - Subjects in the audiology fit group will have one audiology appointment approximately
 2 weeks after being fit. This will give them a chance to have questions answered and for
 fine tuning adjustments to programming as needed.
 - Both groups have access to online rehabilitation programs such as Angelsound, if they wish to use it.
- Second visit One month later
 - Subjects in the self-fit group answer the MDHearing questionnaire.
 - Perform Quick SIN on subjects in both groups. Compare results for statistically significant differences.
 - Ask subjects to complete the Abbreviated Profile of Hearing Aid Benefit (APHAB) and Speech, Spatial, and Qualities of Hearing Scale (SSQ-12). Compare results for statistically significant differences.
 - Perform Real Ear on all subjects using their preferred settings.
 - Compare overall gain settings in relation to hearing loss in both groups. Compare gain settings at 500, 1000, 2000, and 4000Hz as a 4 frequency average in both groups.
 - See Figure 7 in the Bose DeNovo for information on this.

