1.2. Secondary Endpoints

The primary safety endpoint is evaluated by tabulations of adverse events. Another aspect of safety evaluated will be participants' responses to questionnaire items about hearing health safety issues.

2. Clinical Performance Study

The clinical performance study will use a randomized, controlled field trial to examine safety and effectiveness of the subject device, comparing hearing aid outcomes for self-fitting of the device to professional-fitting of the same device.

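### The clinical study's safety endpoint is a tabulation of adverse events, but no listed Part Three step asks about them and the groups' contacts differ, so any by-group table is open to unequal ascertainment of unknown net direction

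*SAP*

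**What the plan says.** SAP section 2 states that the clinical study will "examine safety and effectiveness of the subject device, comparing hearing aid outcomes for self-fitting of the device to professional-fitting of the same device". SAP 2.2 then has a single sentence on safety: "The primary safety endpoint is evaluated by tabulations of adverse events". It does not define an adverse event, name a form or question, set a time window, say whether the table is split by group, or give a criterion for judging it.

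Protocol Part Three describes the study that would supply the data. It plans for "75 subjects with mild to moderate sensorineual hearing loss", and "The subjects are split into two groups". The listed steps are:

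- **First visit:** hearing test, APHAB, SSQ-12, QuickSIN, fitting.
- **Wearing period:** "Subjects wear the hearing aids for one month to acclimate". For one group there is a further contact: "Subjects in the audiology fit group will have one audiology appointment approximately" two weeks after fitting, for questions and fine tuning.
- **Second visit, one month:** QuickSIN, APHAB, SSQ-12 and Real Ear in both groups. In addition, "Subjects in the self-fit group answer the MDHearing questionnaire".

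The entry conditions listed under Subjects include ear drainage, sudden hearing loss, dizziness, cerumen accumulation and "Pain or discomfort in the ear". No later step lists a recheck of any of them.

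**The concern.** The endpoint has no listed source of data. If the schedule is followed as written, an event is recorded only when a subject happens to mention it and someone happens to write it down. The occasions for that differ between groups in two ways: the professional-fit group has an extra mid-period appointment, and the self-fit group has an extra questionnaire. A by-group table would then partly reflect opportunity to report rather than event rates.

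This matters because it is the clinical study's only stated safety endpoint, and the question is whether a device set up without a professional is acceptable. Short-lived problems in the first days of wear, such as canal soreness or discomfort, are the ones most easily lost by one month. A short or empty table could be read as reassurance when nothing in the listed procedures would have filled it.

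**Working it through.** **Set side by side**

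| Part Three step | Self-fit | Professional-fit | Adverse event query listed? |
|---|---|---|---|
| First visit | yes | yes | no |
| About 2 weeks | none | one appointment | no |
| One month: QuickSIN, APHAB, SSQ-12, Real Ear | yes | yes | no |
| One month: MDHearing questionnaire | yes | none | no; items not given |

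SAP 2.3 describes the self-fit satisfaction questionnaire as covering sound quality, cost and ease of use, with no adverse event item mentioned. For the Human Factors study, SAP 1.2 adds questionnaire items on hearing health safety to the event tabulation; the clinical study has no stated equivalent.

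The documents give no event rate or safety sample size, so there is no plan figure to reproduce. What follows is illustration. Group sizes of 37 and 38 come from 75 subjects split in half; every rate is an assumption.

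**1. Effect of the extra appointment alone.** Let each contact detect an existing event with probability d, independently, and let q be the share of events arising before week 2. Suppose the appointment does record events. With equal true rates:

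- self-fit detection = d
- professional-fit detection = q[1 − (1 − d)²] + (1 − q)d = d[1 + q(1 − d)]
- apparent ratio, self-fit to professional-fit = 1 / [1 + q(1 − d)]

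| | d = 0.3 | 0.5 | 0.7 | 0.9 | 1.0 |
|---|---|---|---|---|---|
| q = 0.5 | 0.74 | 0.80 | 0.87 | 0.95 | 1.00 |
| q = 0.75 | 0.66 | 0.73 | 0.82 | 0.93 | 1.00 |
| q = 1 | 0.59 | 0.67 | 0.77 | 0.91 | 1.00 |

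Example with a true rate of 20%, d = 0.5, q = 1: 37 × 0.20 × 0.5 = 3.7 events recorded in self-fit, against 38 × 0.20 × 0.75 = 5.7 in professional-fit.

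**2. Effect of the questionnaire.** Suppose it raises self-fit detection at one month to d*. The ratio becomes d* / {d[1 + q(1 − d)]}. With d = 0.5 and q = 1 the denominator is 0.75, so d* = 0.75 cancels the appointment's effect and d* = 0.9 gives 0.9/0.75 = 1.20. If the appointment records nothing, the ratio is d*/d, for example 0.75/0.5 = 1.50. The sign therefore depends on quantities that the documents do not give.

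**3. What an empty table would mean.** With zero events among n subjects and complete capture, the one-sided 95% upper bound is 1 − 0.05^(1/n): 7.8% for n = 37, 7.6% for n = 38 and 3.9% for all 75. If only half of events are captured (d = 0.5), the bound on the true rate for 37 subjects rises to 0.0778/0.5 = 15.6%.

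**4. Effect of a common query.** If the comparison uses only the same question asked at the same time in both groups, both are detected with the same d, and the expected ratio is 1.00 when true rates are equal.

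**The case against.** A reader might infer that the plan's between-group safety table is biased, and biased towards self-fitting by construction. The documents do not support that, for three reasons.

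- SAP 2.2 specifies tabulation only. Non-inferiority is set for APHAB, SSQ12 and QuickSIN, not for safety. A by-group table is a fair inference from the comparative aim in SAP section 2, but it is not stated.
- The 2-week appointment is described as serving questions and fine tuning. Nothing says that it records adverse events. If it records none, the under-count in step 1 disappears; it also disappears if one-month capture is complete.
- The self-fit questionnaire could raise self-fit counts, so the direction is open.

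Large contrasts are also easy to produce by choice of inputs. With 37 per group, 20% early events, 90% detection at 2 weeks and 25% recall at one month, the expected counts are 37 × 0.20 × 0.25 = 1.9 against 37 × 0.20 × (1 − 0.1 × 0.75) = 6.8. At 75% recall they are 5.6 against 7.2. None of those rates is in the documents.

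Silence is also not proof of absence. The protocol is terse and its final date precedes the SAP's, and a case report form or safety procedure may exist elsewhere. Both groups attend in person at one month for Real Ear, which is an equal contact, though not a documented check.

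These points stand, and they limit the conclusion to a risk. They do not supply a collection step or make the contacts equal. If only a pooled table is intended, the absence of a listed query still leaves a low count uninterpretable.

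**Conclusion.** The point holds as a risk, not as a demonstrated bias. A primary safety endpoint is named without a definition or a listed means of collection, and scheduled contacts differ between groups in two ways. The appointment, if events are noted there, would tend to under-count self-fit events relative to professional-fit; the questionnaire could act the other way. Net direction and size are unknown. The 0.59 to 1.00 ratios describe the first mechanism alone, under assumed detection, independence between contacts and equal true rates.

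The more certain conclusion is about interpretation: few or no recorded events could not be taken as evidence of safety, because the listed procedures do not ask and because 37 or 38 subjects per group leave wide bounds even with full capture. The subjective-benefit endpoint is unaffected. The change should be made, and it concerns data collection and reporting only.

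**What to change.** **Protocol Part Three, second visit.** Add one fixed adverse event checklist, asked in the same words in both groups, before other testing, covering the whole period since fitting. Include the ear conditions already listed under Subjects, irritation or discomfort, and an open question.

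**SAP 2.2.** Define an adverse event. Tabulate all events by group, with exact confidence intervals for the proportion of subjects with at least one event, and report exposure time from fitting to second visit, since SAP section 4 allows delayed appointments. Show each event's source: common checklist, 2-week appointment or spontaneous report. Base the between-group comparison on the common checklist, and keep events from other sources in the table so that none is lost from the safety endpoint.

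**Optional.** A remote query of both groups at about 2 weeks would shorten recall. It also adds contact to the self-fit condition under test, so it is not needed to repair the main gap.

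**If data collection is already complete** (the SAP speaks of recruitment in the past tense), state how events were captured in each group, show their source, and draw no safety conclusion from a between-group difference or from a low count. If a safety form already exists, cite it in SAP 2.2.

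**Cost.** A one-page form, a few minutes at an existing visit and a few sentences in the SAP. More minor events will be recorded. Recall over a month stays imperfect, but it is asked for in the same way in both groups.

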2.3. Secondary Endpoints and Other Effectiveness Measures

The Clinical study will have the following secondary endpoints: speech-in-noise (objective) aided benefit, self-fit user satisfaction, appropriateness (or validity) and reliability of self-fitting method, and robustness of the personalization process to estimate hearing sensitivity for self-fitting using the MDHearing app.

Objective benefit will be considered acceptable if self-fit users have significantly non-inferior benefit scores for speech in noise performance on the QuickSIN compared with the professionally-fit group.

Quick SIN will be performed at two presentation levels: 70 dB HL and Most Comfortable Loudness Level (MCL).

Self-fit participants' satisfaction with sound quality, cost of devices, and ease of device use is evaluated by questionnaire. Sound quality and device cost is considered satisfactory if a majority of respondents are "satisfied" or "very satisfied" according to questionnaire responses; ease of use is considered satisfactory if a majority of questionnaire responses indicate that the hearing aids were easy to operate or that they were able to operate the devices.

The reliability and validity endpoints for in-lab hearing aid performance testing are probe-microphone measures of hearing aid output in the ear canal. The self-fitting method is considered to be reliable if average mean absolute differences (MAD) in the real ear aided response (REAR) measured from 500-4000 Hz after each experimental trial (or run) of user-based self-fitting is 5 dB or less with significance testing. The REAR of professionally-selected hearing aid settings achieved as part of the initial fitting of the hearing aids for professional-fit group participants will be evaluated for proximity to NAL-NL2 prescriptive targets at the respective test frequencies, and amplification will be deemed adequate for the intended user population (adults with mild to moderate hearing loss) if a subjectively close approximation to targets, on average, is achieved.

Participants' hearing levels in each ear from 500-6000 Hz as measured in a quiet room using the MDHearing app installed on a smartphone or tablet (i.e., the personal profile) is compared to their "gold standard" audiometric pure tone thresholds obtained by a clinician using an audiometer in a double-walled sound-treated booth to evaluate the robustness of the personalization process for estimating hearing sensitivity using the MDHearing app; this endpoint will be met if the average difference between personal profile and audiogram is within 10 dB, with a 95% confidence interval.

3. Software

All analyses will be performed using an established statistical computing software (MATLAB, R, JMP).

4. Data Collection

Due to the COVID-19 pandemic, it is understood some subjects may not be able to attend their appointments as scheduled. In that case, subjects will be scheduled as soon as they are able to safely attend appointments. Missing data will be noted as such.

5. Data Use

Human factors endpoints will be used to determine if the current user manual and/or MDHearing app need to be adjusted to ensure user success and safe operation of the devices.

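### Ease of use can be declared satisfactory on ability to operate alone, so a pass does not show that most self-fit users found the aids easy; the counting unit is also unclear.

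*SAP*

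**What the plan says.** SAP section 2.3 lists self-fit user satisfaction among the secondary endpoints and gives it three facets: "Self-fit participants' satisfaction with sound quality, cost of devices, and ease of device use is evaluated by questionnaire".

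The three facets are not judged alike:

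- **Sound quality and cost:** "Sound quality and device cost is considered satisfactory if a majority of respondents are 'satisfied' or 'very satisfied' according to questionnaire responses".
- **Ease:** the bar is reached when "a majority of questionnaire responses indicate that the hearing aids were easy to operate or that they were able to operate the devices".

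In the protocol, the questionnaire is given at the second visit, one month after fitting: "Subjects in the self-fit group answer the MDHearing questionnaire". It does not reproduce the questionnaire. Neither document gives the number of ease items, their wording, a denominator or an interval for this facet. SAP section 4 says of missing data only that it will be noted.

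**The concern.** Being able to operate a device and finding it easy to operate are different results. A participant who manages the app only with difficulty has answered the ability question truthfully and has not reported ease. Under the SAP rule that answer counts towards success for ease.

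The sentence also changes its unit, from respondents for sound quality and cost to questionnaire responses for ease. If several items bear on ease, a majority of responses and a majority of people need not agree.

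At stake is a wrong statement on one facet of a secondary endpoint: the trial could report ease of use as satisfactory when most self-fit users did not find the aids easy. For a device whose case rests on users fitting it themselves, readers will take that statement at face value.

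**Working it through.** The documents give no sample size, power or expected rate for this facet, so there is no planned figure to reproduce. The check has a logical part and an illustrative part.

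**Step 1: what the wording allows (no assumed figures).** Let E be the share answering 'easy' and A the share answering 'able' but not 'easy'. With one answer per person, the SAP rule passes when E + A is above 50%. It does so with E = 0 if A is above 50%. A criterion that matched its label would need E above 50%.

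**Step 2: inputs for the illustration.**

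- Part Three enrols "75 subjects with mild to moderate sensorineual hearing loss".
- "Half of the subjects take the MDHearing personalization profile", so the self-fit group is 75/2 = 37.5, that is 37 or 38 people.
- A majority is 19 of 37 or 20 of 38.
- Assumed: every self-fit participant answers, one answer each, and the rates of E and A shown below. The documents give none of these.

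**Step 3: probability of a pass.** For n = 37, P(pass) = Σ C(37, x) pˣ (1 − p)³⁷⁻ˣ, summed over x = 19 to 37. Here p = E + A under the SAP rule, and p = E if only 'easy' counts.

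| E (assumed) | A (assumed) | P(pass), SAP rule | P(pass), 'easy' only |
|---|---|---|---|
| 10% | 80% | >0.999 | <0.0001 |
| 20% | 50% | 0.995 | <0.0001 |
| 30% | 40% | 0.995 | 0.005 |
| 40% | 40% | >0.999 | 0.108 |

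For n = 38 with a pass at 20, the 30%/40% row becomes 0.992 against 0.003, so the odd participant does not matter.

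**Step 4: can the SAP rule fail?** Yes. For n = 37, P(pass) is 0.108, 0.500, 0.892 and 0.995 when E + A is 40%, 50%, 60% and 70%.

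**Step 5: the counting unit.** With one ease item, responses and respondents give the same count. With two items pooled over 37 people there are 74 responses. If one person is positive on both and the other 36 on one each, the total is 2 + 36 = 38 of 74. That is a majority of responses, although only 1 of 37 people is positive on more than half of the items. The divergence is possible; the documents do not show whether it would arise.

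**The case against.** The case on the other side has real substance.

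- **Pooling is not stated.** A reader might infer that 'able' answers are pooled with 'not easy' answers and outvote them. The SAP does not say so. The sound-quality and cost clause also refers to questionnaire responses, so the change of noun may be loose drafting. This stands: the supportable claim is ambiguity.
- **The questionnaire is not shown.** 'Easy' and 'able' could be categories of one item, separate items, or paraphrases. This stands, and it is why the figures above are only illustrations.
- **Wearing is not operating.** A reader might infer that the rule can hardly fail, because "Minimum of 8 hours per day usage is required" for a month beforehand and, at entry, "Subjects must have and be able to use a smartphone that is compatible with the MDHearing app". These conditions make a high rate of ability plausible among those who answer. They do not establish it: someone can wear the aids all day and still be unable to change the app's settings. Step 4 shows that the rule fails more often than not if fewer than half can operate the aids.
- **Ability is a useful result.** SAP section 1.1 defines usability in the human factors study by ability to complete tasks. That supports reporting ability here too. It does not support reporting it as ease.

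None of this removes the 'or', and nothing elsewhere in the documents tightens it.

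**Conclusion.** The point holds in a limited form. As written, ability alone can satisfy the ease criterion, so a pass does not show that most self-fit users found the aids easy. This follows from the wording and needs no assumed rate. The counting unit is unclear, which matters only if there is more than one ease item.

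The size depends on unknown rates. The contrast of 0.995 with 0.005 rests on an assumed 30% 'easy' and 40% 'able only', one answer per person and full response from 37 people. If most users do find the aids easy, both rules are likely to pass and the reported conclusion would be the same.

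The documents do not support saying that the rule cannot fail or that responses are pooled. Nor does the point touch the primary endpoint, which rests on the APHAB and SSQ12. It is minor: ease is one of three facets of a secondary endpoint assessed in the self-fit group only.

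**What to change.** Reword the ease clause in SAP section 2.3 so that:

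1. ease of use is satisfactory if a majority of self-fit respondents, each counted once, rate the aids easy to operate on a named item;
2. the proportion is given with an exact 95% interval;
3. ability to operate is a separate descriptive line that does not count towards success;
4. the number not answering is reported, with a sensitivity figure that uses all allocated self-fit participants as the denominator.

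The interval is informative here because a bare majority is weak evidence: its lower limit exceeds 50% only from 25 of 37 (67.6%) or 26 of 38 (68.4%). It is proposed for reporting, not as a further hurdle.

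The cost is a short SAP edit. No new visit or test is needed, provided the questionnaire records 'easy' and 'able' separately. The rule's wording suggests that it does, but the sponsor must confirm it. If answers are already in hand, both figures can be reported and the change labelled. The downside is that the reported ease figure may be less favourable.

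### Validity of self-fitting is a real-ear secondary endpoint in SAP 2.3, but its only comparison with NAL-NL2 targets uses the professional-fit group, and the only self-fit real-ear criterion measures repeatability, not accuracy

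*SAP*

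**What the plan says.** SAP 2.3 lists "appropriateness (or validity) and reliability of self-fitting method" among the secondary endpoints and fixes how they are measured: "The reliability and validity endpoints for in-lab hearing aid performance testing are probe-microphone measures of hearing aid output in the ear canal". Two real-ear rules follow.

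- **Reliability.** Real ear aided response (REAR) is measured after each run of user-based self-fitting. The mean absolute difference (MAD) between runs, averaged over 500 to 4000 Hz, must be 5 dB or less, with significance testing.
- **Closeness to target.** "The REAR of professionally-selected hearing aid settings achieved as part of the initial fitting of the hearing aids for professional-fit group participants" is compared with NAL-NL2 targets. Amplification counts as adequate for the intended users "if a subjectively close approximation to targets, on average, is achieved".

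A further rule in SAP 2.3 compares app-measured hearing levels with clinic audiometry: "this endpoint will be met if the average difference between personal profile and audiogram is within 10 dB", with a 95% confidence interval.

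Protocol Part Two is headed "Laboratory Evaluation of Validity of MDHearing Self-Fitting Method". Users adjust the aids during each of three passages, and real-ear measurements follow each one: "Gain results at 500, 1000, 2000, and 4000Hz for a 60dB input will be recorded". The analysis listed is "The differences between gain for each frequency will be evaluated per subject", with a worked example.

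Protocol Part Three, Second visit, schedules real-ear measurement for everyone at preferred settings. It asks for two comparisons between the groups: overall gain relative to hearing loss, and the four-frequency average gain. It gives no test, margin or criterion and refers to a figure in an outside document. The SAP does not mention this comparison.

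**The concern.** A validity endpoint for a self-fitting method should ask whether the output that self-fit users end up with is close to a standard, either the prescriptive target or what a professional achieves. In SAP 2.3 the target comparison is made in the other arm, at initial fitting, on settings chosen by a professional. That can show that the device is able to reach target. It does not include the app's own fitting or the changes that self-fit users make to volume, bass, mid and treble. It also leaves out self-chosen tubing and tips; Part Three gives that choice to half the participants and implies, without stating it, that they are the self-fit half.

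Followed as written, the SAP could support a statement that self-fitting is valid without comparing any self-fit ear-canal output with a target or with the professional-fit group.

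**Working it through.** **1. The rules side by side**

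| Rule | Whose data | Compared with | Criterion |
|---|---|---|---|
| SAP 2.3, reliability | Self-fit, after user adjustment | The user's own other runs | MAD of 5 dB or less |
| SAP 2.3, target | Professional-fit, initial fitting | NAL-NL2 | Subjective, no dB tolerance |
| SAP 2.3, app thresholds | App-measured hearing levels | Audiogram | Average within 10 dB |
| Protocol Part Two | Self-fit, after user adjustment | The user's own other runs | None |
| Protocol Part Three, Second visit | Both groups, preferred settings | Each other, and hearing loss | None stated here |

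No row has self-fit real-ear output, an external standard and a stated criterion together.

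**2. Reproduce the protocol's example**

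Inputs (Part Two table, dB at 500, 1000, 2000 and 4000 Hz): run 1 = 15, 18, 20, 23; run 2 = 17, 19, 22, 22; run 3 = 14, 18, 19, 24.

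Per-frequency deviation = (|run 2 − run 1| + |run 3 − run 2|) / 2:

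- 500 Hz: (2 + 3)/2 = 2.5
- 1000 Hz: (1 + 1)/2 = 1
- 2000 Hz: (2 + 3)/2 = 2.5
- 4000 Hz: (1 + 2)/2 = 1.5

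Total = (2.5 + 1 + 2.5 + 1.5)/4 = 1.875 dB, which matches the stated 1.9 dB. Using all three pairs of runs instead gives 1.5 dB, so the example uses consecutive runs.

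Mean gain = (76 + 80 + 75)/12 = 19.25 dB.

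**3. What the repeatability rule cannot see**

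For any constant c, |(x + c) − (y + c)| = |x − y|. Take c = −10 dB, a hypothetical value, in every cell. Mean gain becomes 9.25 dB; the deviation stays at 1.875 dB (1.5 dB for all pairs), inside the 5 dB limit. Shifts of −15, +10 and +15 dB also leave it unchanged.

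**4. Who is in the target comparison**

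Self-fit participants in Part Three: half of 75, so 37 or 38. Number compared with NAL-NL2: 0. Part Two: 0 of 75. Part Two yields 75 × 3 × 4 = 900 self-fit gain values, counting one ear each (the number of ears is not stated). The only use listed for them is differences between runs.

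**5. Precision available if self-fit data are used**

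The documents give no SD, so 4 to 10 dB is assumed, with no dropout. Half-width of the 95% CI:

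- Self-fit mean signed deviation, n = 38: t(0.975, 37) × SD/√38 = 0.329 × SD, or 1.3 to 3.3 dB.
- Part Two, n = 75: t(0.975, 74) × SD/√75 = 0.230 × SD, or 0.9 to 2.3 dB.
- Between groups, 38 v 37: 1.993 × SD × √(1/38 + 1/37) = 0.460 × SD, or 1.8 to 4.6 dB before any gain from covariate adjustment.

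These figures describe the proposed report. They do not measure the flaw.

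**The case against.** A reader might infer that no rule evaluates self-fit real-ear output after user adjustment. The documents contradict that. The MAD rule does so, in the sentence just before the professional-fit comparison. A reader might also infer that no comparison of self-fit with professional-fit output was planned. That is wrong too: the second visit measures both groups at preferred settings, compares four-frequency gain, and relates overall gain to hearing loss. What is missing is an accuracy criterion or analysis in the SAP.

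Further points for the plan:

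- **An indirect argument exists.** The app embeds NAL-NL2, its thresholds must average within 10 dB of the audiogram, the device is checked against target in professional hands, and self-fit runs must repeat. This supports the app's starting prescription. It does not reach the output after users have adjusted it.
- **The outside figure may hold a criterion.** It may. It is not available here, and the SAP does not refer to it.
- **The target sentence claims device adequacy, not validity of self-fitting.** On that reading, validity has no rule at all. If instead it is the validity rule, its data come from the wrong arm. The gap remains either way.
- **The offset illustration is true by algebra.** Agreed. It shows only what the rule cannot detect and says nothing about how likely an offset is.
- **Departure from target may be preference.** This stands. It limits what any accuracy analysis can conclude and argues against treating deviation as pure fitting error.
- **The stakes are limited.** This also stands. The primary questionnaires and QuickSIN compare the groups directly and are unaffected.

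**Conclusion.** The concern holds as a gap in one secondary endpoint and should be fixed. No rule in the SAP tests the accuracy of self-fit real-ear output against NAL-NL2 or against the professional-fit group. The protocol's second-visit comparison comes closest but has no stated test or criterion in these documents.

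The conclusion rests on the text and on the participant counts, not on the assumed offset or SDs. It is subject to what the outside figure may contain. It does not show that self-fit output is wrong, and the documents give no data from which to infer that.

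**What to change.** Carry the second-visit comparison into SAP 2.3 as the validity analysis.

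1. From the second-visit real-ear data, report signed and absolute deviation from NAL-NL2 at 500, 1000, 2000 and 4000 Hz in both groups, with 95% CIs. Derive targets from audiometer thresholds at the recorded input level. Both forms are needed because absolute deviation rises with spread alone: it averages 0.798 × SD for an unbiased normal variable.
2. Report the self-fit minus professional-fit difference in four-frequency output, adjusted for the four-frequency threshold average, with a 95% CI.
3. State the real-ear quantity used (the protocol says gain, the SAP says REAR) and match the target to it.
4. State that settings are user-preferred and that access to adjustments differs by arm, so deviation mixes preference with fitting error.
5. Use the Part Two self-fit runs, against targets for their 60 dB input, as supporting evidence.
6. Limit the professional-fit initial-fitting result to device adequacy, and confirm when that REAR is measured.
7. If the outside figure contains a criterion, write it into the SAP. A pass/fail margin is optional and needs its own justification. Without one, report validity descriptively and do not declare it met.

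The cost is SAP wording and a small analysis of measurements already scheduled. It depends on second-visit results having been kept with their input level, which the protocol does not state. The validity statement may also prove less favourable than under the current text.
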